8. PREEXISTING MEDICAL CONDITIONS

A preexisting medical condition is one that is present at the screening visit for this study. Such conditions should be recorded on the General Medical History and Baseline Conditions eCRF.

A preexisting medical condition should be recorded as an adverse event only if the frequency, severity, or character of the condition worsens during the study. When recording such events on the Adverse Event eCRF, it is important to convey the concept that the preexisting condition has changed by including applicable descriptors (e.g., "more frequent headaches").

9. WORSENING OF CHRONIC HEPATITIS B

Lack of efficacy in terms of changes in HBsAg does not qualify for adverse event in this study.

Medical occurrences or symptoms of deterioration in the course of chronic hepatitis B should be recorded as an adverse event if judged by the Investigator to have unexpectedly worsened in severity or frequency or changed in nature at any time during the study. When recording an unanticipated worsening of Chronic Hepatitis B on the Adverse Event eCRF, it is important to convey the concept that the condition has changed by including applicable descriptors (e.g., Progression of Chronic Hepatitis B).

Hepatitis B virological breakthrough, hepatitis B virological relapse, and abnormal liver function tests (see Section 8.3.8) should be reported as adverse events.

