8.3.6 Adverse Events of Special Interest

Adverse events of special interest are required to be reported by the Investigator to the Sponsor immediately (i.e., no more than 24 hours after learning of the event; see Appendix 2 for reporting instructions).

Adverse events of special interest for this study include the following:

- Cases of elevated ALT or AST (> 3 × ULN and > 3 × baseline) in combination with either an elevated total bilirubin (> 2 × ULN) or clinical jaundice (Potential Hy's law)
- ALT or aspartate aminotransferase (AST) elevations ≥ 10 × ULN
- Suspected transmission of an infectious agent by the study treatment, as defined below:
 - Any organism, virus, or infectious particle (e.g., prion protein transmitting transmissible spongiform encephalopathy), pathogenic or non-pathogenic, is considered an infectious agent. A transmission of an infectious agent may be suspected from clinical symptoms or laboratory findings that indicate an infection in a participant exposed to a medicinal product. This term applies only when a contamination of the study treatment is suspected.
- Grade ≥3 hematology lab abnormalities (e.g., lymphopenia, neutropenia, leukopenia)
- Severe/serious injection site reactions and/or injection reactions

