8.3.7 Disease-Related Events Not Qualifying as Adverse Events

The following disease-related events (DREs) can be observed in participants with CHB:

ALT or AST increase < 10 × ULN with preserved hepatic function

Because these events may be associated with the disease under study, they should not be reported according to the standard process for AEs. ALT increase > 3 × ULN should be managed according to Section 8.3.8.3.

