8.3.8.3 Management of Elevated Alanine Aminotransferase (ALT) Levels

The initial study population consists of CHB participants who are virally suppressed following > 12 months of NUC treatment. The majority of these participants (90%) have normal ALT levels, while approximately 10% have ALT levels within 1–2×ULN at baseline (Marcellin et al 2019).

For this study, close monitoring will be initiated if ALT elevations exceed $> 3 \times ULN$.

ALT elevations during treatment

- ALT elevation with preserved hepatic function (e.g., no significant changes in bilirubin, International Normalized Ratio [INR]/prothrombin time [PT], albumin, and/or alkaline phosphatase [ALP]):
 - ALT 3–10×ULN: *Repeat ALT, LFTs (including total bilirubin, direct bilirubin, AST, ALP, albumin), coagulation (INR, PT), and PD parameters (HBV DNA, HBsAg, quantitative HBeAg) every week until ALT< 3 × ULN.
 - ALT > 10 × ULN: Immediately interrupt NMEs and continue NUC treatment.
 *Repeat ALT, LFTs, coagulation, and PD parameters #twice weekly until ALT level < 10 × ULN, then weekly until ALT < 3 × ULN. Consider re-introducing NME therapy on a case-by-case basis based on subsequent lab results. The Medical Monitor is available to the Investigator to answer any medical questions.
- ALT elevation accompanied by declining liver synthetic and excretory functions (total bilirubin > 2×ULN, or albumin <3.0 g/dL, or INR >1.5) or other signs of hepatic impairment (severe fatigue, vomiting):
 - Immediately discontinue NMEs and continue NUC treatment.
 - *Repeat ALT, LFTs, Coagulation, and PD parameters #twice weekly until levels return towards baseline levels or normal range
 - o Investigate the participant for potential etiologies of the laboratory changes.
 - If alternative reasons/diagnoses cannot explain the laboratory changes, potential drug-induced liver injury (DILI) will be considered.

^{*}Frequency of monitoring may need to be adjusted based upon clinical scenario and severity of injury. * As the central laboratory results generation and reporting will take time, for

participant safety monitoring an additional local laboratory tests may be performed at the same time as the central laboratory test, and decision-making may be based on local laboratory results.

For marked and/or persistent ALT elevations, collect a spare serum sample (to allow retrospective evaluation of potential etiologies) and consider liver biopsy on a case-by-case basis (if deemed clinically relevant).

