4. ABNORMAL LABORATORY VALUES

Not every laboratory abnormality qualifies as an adverse event. A laboratory test result should be reported as an adverse event if it meets any of the following criteria:

- Accompanied by clinical symptoms.
- Results in a change in study treatment (e.g., dose modification, treatment interruption, or treatment discontinuation).
- Results in a medical intervention (e.g., potassium supplementation for hypokalemia) or a change in concomitant therapy.
- Clinically significant in the Investigator's judgment.

It is the Investigator's responsibility to review all laboratory findings. Medical and scientific judgment should be exercised in deciding whether an isolated laboratory abnormality should be classified as an adverse event.

If a clinically significant laboratory abnormality is a sign of a disease or syndrome (e.g., alkaline phosphatase and bilirubin 5 times the upper limit of normal [ULN] associated with cholecystitis), only the diagnosis (i.e., cholecystitis) should be recorded on the Adverse Event eCRF.

If a clinically significant laboratory abnormality is not a sign of a disease or syndrome, the abnormality itself should be recorded on the Adverse Event eCRF, along with a descriptor indicating if the test result is above or below the normal range (e.g., "elevated potassium", as opposed to "abnormal potassium"). If the laboratory abnormality can be characterized by a precise clinical term per standard definitions, the clinical term should be recorded as the adverse event. For example, an elevated serum potassium level of 7.0 mEg/L should be recorded as "hyperkalemia."

Observations of the same clinically significant laboratory abnormality from visit to visit should not be repeatedly recorded on the Adverse Event eCRF, unless the etiology changes. The initial severity of the event should be recorded, and the severity or seriousness should be updated any time the event worsens.

5. ABNORMAL VITAL SIGN VALUES

Not every vital sign abnormality qualifies as an adverse event. A vital sign result should be reported as an adverse event if it meets any of the following criteria:

- Accompanied by clinical symptoms.
- Results in a change in study treatment (e.g., dose modification, treatment interruption, or treatment discontinuation).
- Results in a medical intervention or a change in concomitant therapy.
- Clinically significant in the Investigator's judgment.

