6. ABNORMAL LIVER FUNCTION TESTS

The finding of an elevated ALT or AST ($> 3 \times ULN$ and $> 3 \times baseline$) in combination with either an elevated total bilirubin ($> 2 \times ULN$) or clinical jaundice in the absence of cholestasis or other causes of hyperbilirubinemia (Potential Hy's law) is considered to be an indicator of severe liver injury (DILI). Therefore, investigators must report as an adverse event the occurrence of either of the following:

- Treatment-emergent ALT/AST>3×ULN and>3 × baseline, in combination with total bilirubin>2×ULN.
- Treatment-emergent ALT or AST>3×ULN and>3 × baseline, in combination with clinical jaundice.

The most appropriate diagnosis or (if a diagnosis cannot be established) the abnormal laboratory values should be recorded on the Adverse Event eCRF and reported to the Sponsor immediately (i.e., no more than 24 hours after learning of the event) as a AESI (Section 8.3.6) and serious adverse event, if the SAE definition criteria is met.

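### The protocol both exempts and requires adverse-event reporting of ALT 3–10×ULN with preserved hepatic function, so AE counts can depend on which section a site follows

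*Protocol*

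**What the plan says.** **The exemption.** Protocol Section 8.3.7, whose title says it covers events that do not qualify as AEs, lists a single class: "ALT or AST increase < 10 × ULN with preserved hepatic function". The instruction is: "Because these events may be associated with the disease under study, they should not be reported according to the standard process for AEs". The section then sends ALT above 3×ULN onward; it "should be managed according to Section 8.3.8.3".

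**The requirement.** Appendix 3, Section 9 ends with: "Hepatitis B virological breakthrough, hepatitis B virological relapse, and abnormal liver function tests (see Section 8.3.8) should be reported as adverse events". It sets no ALT threshold and makes no exception for Section 8.3.7.

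**The range the two share.** Section 8.3.8.3 has a separate branch for ALT 3–10×ULN with preserved hepatic function. It appears once for the treatment period and again for follow-up.

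**The general laboratory rule.** Appendix 3, Section 4 makes a laboratory result an AE if any one of four triggers is met. One of them is: "Results in a change in study treatment (e.g., dose modification, treatment interruption, or treatment discontinuation". Appendix 2, Section 1 has a similar provision. In the siRNA + PEG-IFN + NUC arm, Appendix 10-Table 2 prescribes a PEG-IFN dose change for persistent ALT of at least 5 and below 10×ULN.

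**The analysis.** SAP 4.5.2 tabulates investigator-reported AEs overall, by grade and causality, and those leading to dose interruption or adjustment. It has no rule that settles how these rises are classified.

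**The concern.** Incidence, nature and severity of AEs, together with laboratory abnormalities, form a secondary endpoint (protocol Table 1; SAP Table 1). If two sites see the same ALT of 6×ULN with normal bilirubin, INR and albumin, one can correctly leave it off the AE form under Section 8.3.7. The other can correctly enter it under Appendix 3, Section 9. The AE table then partly measures which section the site consulted.

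The inconsistency need not cancel between arms. The trial is open-label, and the documents expect ALT rises more with some agents than others. Appendix 13, Section A13.3 calls low-grade transient rises frequent at the highest PD-L1 LNA regimen studied in Phase 1. Appendix 10, Section A10.10.1 gives ALT elevation as a common reason for PEG-IFN dose modification. With about 30 participants per arm, a few discretionary entries are visible in a percentage.

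**Working it through.** This is a comparison of instructions. The plan states no figure to reproduce.

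**Step 1: find where the instructions overlap.**

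| ALT finding | Section 8.3.7 | Other protocol sections | Conflict? |
|---|---|---|---|
| Below 3×ULN, function preserved | Exempt | Appendix 3, Section 9 points to Section 8.3.8, where close monitoring starts above 3×ULN | Not firmly shown |
| 3–10×ULN, function preserved | Exempt | Appendix 3, Section 9 requires an AE; Section 8.3.8.3 covers the range | Yes |
| Persistent 5 to <10×ULN with PEG-IFN dose change, function preserved | Exempt | Appendix 3, Section 4 also requires an AE, through its treatment-change trigger | Yes, on a second ground |
| At or above 10×ULN | Outside the exemption | AESI under Section 8.3.6: "ALT or aspartate aminotransferase (AST) elevations ≥ 10 × ULN" | No |
| Hy's law pattern | Function not preserved, so outside the exemption | Appendix 3, Section 6: "Therefore, investigators must report as an adverse event the occurrence of either of the following" | No |

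The exempt class covers ALT or AST. Section 8.3.8.3 sets its thresholds on ALT, so the firm overlap is for ALT.

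**Step 2: look for a reading that removes the conflict.**

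- *Appendix 3, Section 9 might mean only the Hy's law events*, because Appendix 3, Section 6 carries the abnormal-liver-test heading. But the sentence points to Section 8.3.8, which is broader.
- *Section 8.3.7 might only redirect events to a different reporting route.* But its title says they are not AEs, and it names no other route.
- *One section might override the other.* No such rule was found. The precedence statement in Section 5 concerns eligibility criteria only.

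**Step 3: trace the affected outputs.** SAP 4.5.2 outputs depend on what sites enter as AEs. The DAIDS laboratory shift tables, liver-test profiles and eDISH plot in SAP 4.5.3.1 do not. The source of the ALT-increased summary (DAIDS grade 1 or higher) is not stated, but it sits in the laboratory section.

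**Step 4: scale.** For an arm of about 30, one participant counted or omitted changes incidence by 1/30 = 0.033, or about 3.3 percentage points. The documents do not give the number of disputed events.

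**The case against.** The best case on the other side is that the damage is bounded. The serious liver events are reportable under every section. The study is exploratory and descriptive, with no hypothesis test. Laboratory abnormalities are a named part of the same endpoint, ALT is measured centrally, and SAP 4.5.3.1 already plans shift tables, an ALT-increased summary, Hy's law incidence, profiles and eDISH. SAP 4.5.1 flags dose modifications from administration data whether or not an AE was entered.

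Most of this stands. It rules out any claim that the liver safety assessment as a whole is compromised, and it makes an additional table of ALT cut-points largely a matter of presentation. It does not remove the point. The laboratory outputs carry no investigator causality and cannot supply the count of AEs leading to dose change. The DAIDS shifts also cover only the treatment period, whereas AEs are collected to the last follow-up visit.

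Three stronger readings are tempting and not supported:

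- A reader might infer that every rise below 10×ULN is in conflict. The exemption applies only with preserved function, and the firm overlap starts at 3×ULN.
- A reader might infer that Appendix 3, Section 4 catches every rise of 3–10×ULN. It applies only when a trigger is met. For this range Section 8.3.8.3 asks for repeat testing, and the PEG-IFN dose change is the concrete prescribed case.
- A reader might take the roughly 11% and 17% above 5×ULN in Appendix 13, Section A13.3 as a range, giving 0.11 × 30 = 3.3 to 0.17 × 30 = 5.1 participants per PD-L1 LNA arm. Those figures compare two regimens and are not a range for trial participants. They also include anyone at or above 10×ULN or with declining function, where there is no conflict, and omit rises of 3 to 5×ULN.

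**Conclusion.** This is an internal inconsistency in the protocol. ALT 3–10×ULN with preserved hepatic function is excluded from AE reporting by Section 8.3.7 and required by Appendix 3, Section 9. When the rise changes treatment, Appendix 3, Section 4 adds a second requirement against the same exemption. AE incidence, AEs by grade and causality, and AEs leading to dose change can therefore differ by site and by arm for reasons unrelated to the drugs.

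The direction and size of any distortion cannot be derived from the documents; 3.3 percentage points per participant is a scale, not an estimate. The conclusion rests on reading the cross-reference to Section 8.3.8 as including Section 8.3.8.3, and on no precedence rule existing in material outside the protocol and SAP, such as site training or eCRF guidance. The point should be fixed but does not threaten the primary analysis.

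**What to change.** Reconcile Section 8.3.7 with Appendix 3, Sections 4 and 9 into one AE-reporting rule for ALT/AST 3–10×ULN with preserved hepatic function. The rule should state explicitly what happens when the rise leads to a change in study treatment. The sponsor decides which way it goes.

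Notify all sites, and apply the rule consistently to events already recorded in ongoing arms. Protocol Appendix 6-Table 1 lists arms 1, 3, 4, 5 and 7 as ongoing, and SAP Table 8 adds arms 8 and 9.

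The cost is a wording amendment, a site letter and a retrospective query of recorded ALT/AST rises in this range. The query is the real burden, because new wording alone would not harmonise entries already made. No new samples or visits are needed.

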10. HOSPITALIZATION OR PROLONGED HOSPITALIZATION

Any adverse event that results in hospitalization or prolonged hospitalization should be documented and reported as a serious adverse event (per the definition of serious adverse event in Appendix 2), except as outlined below.

An event that leads to hospitalization under the following circumstances should not be reported as an adverse event or a serious adverse event:

- Hospitalization for respite care
- Planned hospitalization required by the protocol (e.g., for study treatment administration or insertion of access device for study treatment administration)
- For administrative reasons (e.g., participant lives far away and is kept in the clinic/hospital for participant and/or site convenience)
- Hospitalization for a preexisting condition (not CHB), provided that all of the following criteria are met:
 - The hospitalization was planned prior to the study or was scheduled during the study when elective surgery became necessary because of the expected normal progression of the disease.
 - The participant has not suffered an adverse event.

An event that leads to hospitalization under the following circumstances is not considered to be a serious adverse event, but should be reported as an adverse event instead:

 Hospitalization for an adverse event that would ordinarily have been treated in an outpatient setting had an outpatient clinic been available.

Appendix 4 Clinical Laboratory Tests

The tests detailed in Appendix 4-Table 1 below will be performed by the central laboratory, with the exception of urinalysis, alcohol and drugs of abuse screen, which will be performed locally.

Local laboratory results are only required in the event that the central laboratory results are not available in time for either study treatment administration (including for the randomization/dosing day) and/or a response evaluation. If a local sample is required, it is important that the sample for central analysis is obtained at the same time. Additionally, if the local laboratory results are used to make either a study treatment decision or a response evaluation, the results must be captured in source documentation and entered as a comment into the eCRF.

Protocol-specific requirements for inclusion or exclusion of participants are detailed in Sections 5.1 and 5.2, respectively, of the protocol.

Additional tests may be performed at any time during the study as determined necessary by the Investigator or required by local regulations.

Appendix 4-Table 1 Protocol-Required Safety Laboratory Assessments

Laboratory Assessments	Parameters
Hematology	 Leucocytes, erythrocytes, hemoglobin, hematocrit, platelets, differential count (neutrophils, eosinophils, basophils, monocytes, lymphocytes), mean corpuscular hemoglobin (MCH), mean corpuscular hemoglobin concentration (MCHC) and glycated hemoglobin (HbA1c).
Clinical Chemistry	 Sodium, potassium, chloride, bicarbonate, phosphorus, calcium, magnesium, urea, uric acid, blood urea nitrogen (BUN), creatinine and cystatin C, estimated glomerular filtration rate (eGFR), glucose, total protein, albumin, total and direct bilirubin, alkaline phosphatase (ALP), ALT, AST, gamma-glutamyl transferase (GGT), alpha fetoprotein, glutamate dehydrogenase (GLDH), lipase, creatine kinase/creatine phosphokinase (CK/CPK), LDH and amylase.
Lipids	 Total cholesterol, low-density lipoproteins (LDL) cholesterol, high-density lipoproteins (HDL) cholesterol, triglycerides.
Thyroid Function Tests	 TSH, free T3 and free T4.
Coagulation	 INR, activated partial thromboplastin time, PT.
Viral Serology	 HIV (specific tests HIV-1 antibody, HIV-1/2 antibody, HIV-2 antibody), hepatitis A virus (HAV IgM antibody), hepatitis B surface antigen (HBsAg), hepatitis C virus (HCV) antibody, hepatitis D virus (HDV) antibody, hepatitis E virus (HEV) antibody.
Pregnancy Test	 All women of childbearing potential (including those who have had a tubal occlusion/ligation) will have a blood pregnancy test at screening. Urine pregnancy tests will be performed at subsequent visits according to SOAs. If a urine pregnancy test is positive, it must be confirmed by a blood pregnancy test.
Urinalysis	Specific gravity.
	 Dipstick: pH, glucose, protein, blood, ketones, bilirubin, urobilinogen, nitrites, leukocytes.
	If there is a clinically significant positive result (e.g., 2+ or greater for blood, protein or leukocytes) confirmed by a positive repeated sample, urine will be sent to the central laboratory for microscopy and culture. In addition, if there is clinically significant proteinuria (2+ or greater for protein), central laboratory will measure the urine protein: creatinine ratio.
	If there is an explanation for the positive dipstick results (e.g., menses), it should be recorded and there is no need to perform microscopy and culture.
	 Microscopic examination (sediment, red blood cells [RBCs], WBCs, casts, crystals, epithelial cells, bacteria), if blood or protein is abnormal.
Other Screening Tests	 Alcohol and drug screen according to local procedure to include at minimum: amphetamines, barbiturates, cocaine, opiates, cannabinoids, and benzodiazepines.
	 Auto-antibodies (ANA, AMA, ASMA, a-TPO).

Investigators must document their review of each laboratory safety report.

Additional Statistical Considerations for Clinical Laboratory Data

Standard Reference Ranges and Transformation of Data

Potential analysis considerations for analyzing laboratory data includes the use of standard reference ranges and potential transformation of data for specific lab tests.

In this scenario, Roche standard reference ranges, rather than the reference ranges of the Investigator, can be used for specific parameters. For these parameters, the measured laboratory test result will be assessed directly using the Roche standard reference range. Certain laboratory parameters will be transformed to Roche's standard reference ranges.

A transformation will be performed on certain laboratory tests that lack sufficiently common procedures and have a wide range of Investigator ranges, e.g., enzyme tests that include AST, ALT, and alkaline phosphatase and total bilirubin. Since the standard reference ranges for these parameters have a lower limit of zero, only the upper limits of the ranges will be used in transforming the data.

Definition of Laboratory Abnormalities

For all laboratory parameters included in this analysis, there exists a Roche predefined standard reference range. Laboratory values falling outside this standard reference range will be labeled "H" for high or "L" for low in participant listings of laboratory data.

In addition to the standard reference range, a marked reference range has been predefined by Roche for these laboratory parameters. The marked reference range is broader than the standard reference range. Values falling outside the marked reference range that also represent a defined change from baseline will be considered marked laboratory abnormalities (i.e., potentially clinically relevant). If a baseline value is not available for a participant, the midpoint of the standard reference range will be used as the participant's baseline value for the purposes of determining marked laboratory abnormalities. Marked laboratory abnormalities will be labeled in the participant listings as "HH" for very high or "LL" for very low.

